2. INTRODUCTION

This SAP provides the detailed methodology for summary and statistical analyses of the data collected in study B9991001. This document may modify the plans outlined in the protocol; however, any major modifications of the primary endpoint definition or its analysis will also be reflected in a protocol amendment.

A separate SAP will cover the interim analyses for periodic safety review by the External Data Monitoring Committee (E-DMC).

Statistical analyses will be performed using cleaned eCRF data as well as non-CRF data (ie, pharmacokinetic [PK] concentration, anti-drug antibodies (ADA; neutralizing antibody [nAb]), supplemental biomarker data, and tumor assessment results by the Blinded Independent Central Review (BICR)).

The primary analysis will include all data up to a cut-off date which is determined by the number of events (deaths) required for the analysis of Overall Survival (OS) and a minimum follow-up of 12 months after the last patient is randomized. The cut-off date is determined once a data extract (before database lock) is available which indicates that the required number of events for OS in both co-primary populations and the minimum follow-up of 12 months is expected to occur by the cut-off date.

Due to data cleaning activities, the final number of events might deviate from the planned number. The data cut-off date will not be adjusted retrospectively in this case.

2.1. Study Objectives

Primary Objectives

- To demonstrate the benefit of maintenance treatment with avelumab plus best supportive care (BSC) vs. BSC alone in prolonging OS in patients with unresectable locally advanced or metastatic Urothelial Cancer (UC) whose disease did not progress on or following completion of first-line platinum-containing chemotherapy in each co-primary UC patient population: 1) patients determined to have PD-L1-positive tumors (including infiltrating immune cells) by a verified Good Manufacturing Practice (GMP) PD-L1 immunohistochemistry (IHC) test, and 2) all randomized patients.

Secondary Objectives

- To compare the PFS of avelumab plus BSC vs. BSC alone in patients determined to have PD-L1-positive tumors (including infiltrating immune cells) by a verified GMP PD-L1 IHC test, and in all randomized patients.
- To evaluate the anti-tumor activity of avelumab plus BSC and BSC alone according to Response Evaluation Criteria in Solid Tumors (RECIST) v1.1 in patients determined to

have PD-L1-positive tumors (including infiltrating immune cells) by a verified GMP PD-L1 immunohistochemistry (IHC) test, and in all randomized patients.

- To evaluate the overall safety profile of avelumab plus BSC and BSC alone.
- To evaluate the PK of avelumab in each of the co-primary UC patient populations treated with avelumab.
- To assess the immunogenicity of avelumab in each of the co-primary UC patient populations treated with avelumab.
- To evaluate candidate predictive biomarkers of sensitivity or resistance to avelumab in pre-treatment tumor tissue in each of the co-primary UC patient populations treated with avelumab.
- To evaluate the effect of avelumab plus BSC and BSC alone on patient-reported outcomes (PROs) in each of the co-primary UC patient populations.

Exploratory Objectives

[figure not shown]
- To explore the predictive and/or pharmacodynamic (PD) characteristics of peripheral blood and additional tumor tissue biomarkers relevant to the mechanism of action of or resistance to avelumab.

2.2. Study Design

This is a Phase 3, multicenter, multinational, randomized, open-label, parallel-arm efficacy and safety study of avelumab plus BSC compared to BSC alone as a maintenance treatment after completion of first-line platinum-based chemotherapy (gemcitabine + cisplatin or gemcitabine + carboplatin) without evidence of disease progression in adult patients with unresectable locally advanced or metastatic UC.

The study design is illustrated in [Figure 1](#).

Figure 1. Study Design Schema

- a. Allowed first-line chemotherapy regimens are gemcitabine + cisplatin or gemcitabine + carboplatin.
b. Randomization must occur at least 4 and not more than 10 weeks after the last dose of first-line chemotherapy and will be stratified by: best response on 1st-line therapy (CR or PR vs. SD) and metastatic disease site (visceral vs. non-visceral).

CR = complete response; IV = intravenous; PD = progressive disease; PR = partial response; Q2W = every 2 weeks; SD = stable disease

- A total of approximately 668 patients without progressive disease (PD) as per RECIST v1.1 guidelines (ie, with ongoing CR, PR, or SD) after 1st line chemotherapy will be randomized in this study. It is estimated that at least 334 patients with confirmed PD-L1-positive tumors (including infiltrating immune cells) will be randomized in this study.
- Patients will be randomized in a 1:1 ratio into two study arms: avelumab + BSC (Arm A) or BSC alone (Arm B).
- Randomization will be stratified by (i) best response to first-line chemotherapy (CR/PR vs. SD), and (ii) metastatic disease site (visceral vs. non-visceral) at the time of initiating first-line chemotherapy.
- This study is designed with two co-primary populations: 1) patients determined to have PD-L1-positive tumors (including infiltrating immune cells) by a verified GMP PD-L1 IHC test, and 2) all randomized patients.
- Patients must have received at least 4 cycles, but not more than 6 cycles, of a first-line chemotherapy regimen consisting of either gemcitabine + cisplatin or gemcitabine + carboplatin before randomization into this study. No other chemotherapy regimen is allowed as the first line chemotherapy for inclusion in this clinical trial (please see Section 4.1 of the protocol, Inclusion Criteria 2).
- Randomization must occur at least 4 but not more than 10 weeks after the date of administration of the last dose of chemotherapy. Patients will initiate study treatment (Cycle 1 Day 1) within 3 days after randomization.

- Only patients without progressive disease as per RECIST v1.1 guidelines (ie, with ongoing CR, PR, or SD) after 4-6 cycles of chemotherapy will be allowed to be randomized in this study.
 - Post-chemotherapy confirmatory scan(s) (CT/MRI) for eligibility must be performed within 28 days prior to the date of randomization to assess response status following first-line chemotherapy.
 - Based on the post-chemotherapy confirmatory scan(s), the investigator should assess patient eligibility (ie, CR, PR, or SD) before randomization.

3. ENDPOINTS AND BASELINE VARIABLES: DEFINITIONS AND CONVENTIONS

3.1. Primary Endpoint

- Overall Survival (OS).

OS is defined as the time from the date of randomization to the date of death due to any cause.

3.2. Secondary Endpoints

3.2.1. Safety endpoints

- Adverse events (AEs) and laboratory abnormalities as graded by National Cancer Institute (NCI) Common Terminology Criteria for Adverse Events (CTCAE) v4.03; vital signs (blood pressure, pulse rate).

AEs will be graded by the investigator according to CTCAE v4.03 and coded using the Medical Dictionary for Regulatory Activities (MedDRA).

3.2.2. Efficacy endpoints

- Progression-free survival (PFS) based on BICR assessment per RECIST v1.1.
- Investigator-assessed PFS.

PFS is defined as the time from the date of randomization to the date of the first documentation of progressive disease (PD) or death due to any cause, whichever occurs first.

- Objective Response (OR), Time to Tumor Response (TTR), Duration of Response (DR), and Disease Control (DC), as assessed per RECIST v1.1 by BICR and investigator.

OR is defined as complete response (CR), or partial response (PR), according to RECIST v1.1, from the date of randomization, until the date of the first documentation of PD. Both CR and PR must be confirmed by repeat assessments performed no less than 4 weeks after the criteria for response are first met.

DR is defined, for patients with OR, as the time from the first documentation of objective response (CR or PR) to the date of first documentation of PD or death due to any cause.

DC is defined as CR, PR, non-CR/non-PD or stable disease (SD). Both CR and PR must be confirmed by repeat assessments performed no less than 4 weeks after the criteria for response are first met. Criteria for SD and non-CR/non-PD must have been met at least 6 weeks after the date of randomization.

TTR is defined, for patients with an OR, as the time from the date of randomization to the first documentation of objective response (CR or PR) which is subsequently confirmed.

3.2.3. Patient Reported Outcomes endpoints

- Patient-reported bladder cancer symptom, functioning, global quality of life (QOL), and Time to Deterioration (TTD) using the NCCN-FACT FBISI-18; and health status using the EQ-5D-5L.

The NCCN FACT FBISI-18 (a later version of the FACT-BI) was developed to be part of the Functional Assessment of Chronic Illness Therapy (FACIT) system and was specifically created with input from the Food and Drug Administration (FDA) and validated in bladder cancer patients. The NCCN FACT FBISI-18 is designed to be a stand-alone instrument to measure symptoms and QoL in patients with UC and was created using inputs from patients and oncologists. The ‘Disease Related Symptoms-Physical’ subscale of the NCCN-FACT FBISI-18 (FBISI-DRS-P) uses a subset of physical symptoms which are considered to be specific to UC.

The EuroQol EQ-5D-5L is a 6-item patient-completed questionnaire designed to assess health status in terms of a single index value or utility score. There are 2 components to the EuroQol EQ-5D-5L, a Health State Profile which has individuals rate their level of problems (none, slight, moderate, severe, extreme/unable) in 5 areas (mobility, self-care, usual activities, pain/discomfort, and anxiety/depression), and a Visual Analogue Scale (VAS) in which patients rate their overall health status from 0 (worst imaginable) to 100 (best imaginable). Published weights are available that allow for the creation of a single summary score. Overall scores range from 0 to 1, with low scores representing a higher level of dysfunction.

3.2.4. Pharmacokinetic endpoints

- Maximum concentrations (C_{max}) and trough concentrations (C_{trough}) for avelumab.

C_{max} and C_{trough} are calculated after single and multiple dose and at steady-state.

Table 2. PK Parameters to be Determined for Avelumab

Parameter	Definition	Method of Determination
C_{max}	Maximum observed plasma concentration	Observed directly from data
C_{trough}	Pre-dose concentration during multiple dosing	Observed directly from data

3.2.5. Immunogenicity endpoints

- Incidence of anti-drug antibodies (ADA, nAb) against avelumab.

3.2.6. Biomarker endpoints

- Tumor tissue biomarkers including, but not limited to, PD-L1 expression and tumor-infiltrating CD8+ T lymphocytes.

Table 3. Biomarker Definition and Determination

Parameter	Definition	Method of Determination
PD-L1 expression	The number of PD-L1-positive cells and/or qualitative assessment of PD-L1 staining on tumor and inflammatory cells in regions of interest that are defined by tumor cell morphology and the presence or absence of inflammatory cells	Pathologist, assisted by image analysis
Tumor infiltrating CD8+ lymphocytes	The number of CD8+ cells per unit area and the percent of counted cells that are scored as CD8+	Pathologist, assisted by image analysis

3.3. Exploratory Endpoints

- *Biomarkers:* Peripheral blood and additional tumor tissue biomarkers consisting of the levels of cells, deoxyribonucleic acid (DNA), ribonucleic acid (RNA), or proteins that may be related to anti-tumor immune response and/or response to or disease progression on avelumab, such as genes related to IFN- γ or transforming growth factor (TGF)- β .

3.4. Baseline Variables

3.4.1. Study drug, study treatment and baseline definitions

In this study, ‘study drug’ refers to avelumab or BSC and ‘study treatment’ (or ‘treatment arm’) refers to one of the following:

- Arm A = Avelumab + BSC;
- Arm B = BSC alone.

Start and end dates of study treatment:

- For Arm A:
 - The date/time of first dose of study treatment is the earliest date/time of non-zero dosing of the study drug.
 - The date/time of last dose of study treatment is the latest date/time of non-zero dosing of the study drug.

- For Arm B:
 - The date of start of study treatment is defined as the date of Cycle 1 Day 1 (C1D1); a patient is considered to be treated in Arm B if they complete the C1D1 visit.
 - ‘End date of BSC’ (last dose of study treatment) is the date of completion or discontinuation as collected in the ‘Disposition - Treatment Phase’ eCRF page.

Definition of baseline:

Definition of baseline for efficacy and PRO analyses

The last measurement prior to randomization will serve as the baseline measurement for efficacy and PRO analyses. If such a value is missing (since per protocol the first PRO assessment is planned to occur on Cycle 1 Day 1), the last measurement prior to the first dose of study treatment will be used as the baseline measurement except for analyses of tumor assessments data where the baseline assessment would be considered as missing.

Definition of baseline for immunogenicity analyses (Arm A only)

The last available assessment prior to the start of treatment with avelumab is defined as ‘baseline’ result or ‘baseline’ assessment. If an assessment is planned to be performed prior to the first dose of avelumab in the protocol and the assessment is performed on the same day as the first dose of avelumab, it will be assumed that it was performed prior to avelumab administration, if assessment time point is not collected or is missing.

Definition of baseline for safety analyses

The last available assessment prior to the start of study treatment is defined as ‘baseline’ value or ‘baseline’ assessment for safety analyses. If an assessment is planned to be performed prior to the first dose of study treatment in the protocol and the assessment is performed on the same day as the first dose of study treatment, it will be assumed that it was performed prior to study treatment administration, if assessment time point is not collected or is missing. If assessment time points are collected, the observed time point will be used to determine pre-dose on study day 1 for baseline calculation. Unscheduled assessments will be used in the determination of baseline. However, if time is missing, an unscheduled assessment on study day 1 will be considered to have been obtained after study treatment administration.

Patients who start treatment and discontinue from the study on the same day may have two different sets of data collected on study day 1 (one during study and one in the End of Treatment (EOT) visit). Data reported at the EOT visit are not eligible for baseline selection.

If a scheduled pre-dose measurement actually occurred post-dose, then the corresponding measurement will be treated and analyzed similar to an unscheduled post-dose measurement.

Definition of baseline for biomarker analyses

The last measurement prior to first dose of study treatment will serve as the baseline measurement for biomarker analyses. For biomarkers that are planned to be measured on Cycle 1 Day 1, it will be assumed that the measurement was performed prior to study treatment administration, if the assessment time point is not collected or is missing.

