5.4.1. Treatment after Initial Evidence of Radiologic Disease Progression

Immunotherapeutic agents such as avelumab may produce anti-tumor effects by potentiating endogenous cancer-specific immune responses. The response patterns seen with such an approach may extend beyond the typical time course of responses seen with cytotoxic agents, and can manifest as a clinical response after an initial increase in tumor burden or even the appearance of new lesions.

If radiologic imaging shows disease progression as assessed by BICR (or as assessed by Investigator as per Protocol Amendment 6, following the final OS update), after discussion between the Sponsor and Investigator, patients may continue to receive avelumab at the Investigator's discretion if the following criteria are met:

- Absence of clinical signs and symptoms (including worsening of laboratory values) of disease progression.
- No decline in ECOG performance status.
- Absence of rapid progression of disease by radiographic imaging.
- Absence of progressive tumor at critical anatomical sites (eg, cord compression) requiring urgent alternative medical intervention.

Patients who stop avelumab treatment, and then experience radiologic disease progression thereafter, will be eligible for re-treatment with avelumab at the discretion of the investigator and after discussion with the sponsor's medical monitor if 1) no cancer treatment was administered other than BSC since the last dose of avelumab, 2) the patient does not meet the safety withdrawal criteria, and 3) the trial is still open.

As per Protocol Amendment 6, following the final OS update, patients who stop avelumab treatment and subsequently experience radiologic disease progression, will no longer be eligible for re-treatment with avelumab.

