8.2. Reporting Period

For SAEs, the active reporting period to Pfizer or its designated representative begins from the time that the patient provides informed consent, which is obtained prior to the patient's participation in the study, ie, prior to undergoing any study-related procedure and/or receiving study treatment, through and including 90 calendar days after the last administration of the study treatment (Arm A) or 90 days after the EOT visit (Arm B). SAEs occurring to a patient after the active reporting period has ended should be reported to the sponsor if the investigator becomes aware of them; at a minimum, all SAEs that the investigator believes have at least a reasonable possibility of being related to study treatment are to be reported to the sponsor.

AEs (serious and non-serious) should be recorded on the CRF from the time the patient has taken at least 1 dose of study treatment (Arm A) or from Cycle 1 Day 1 (Arm B) through and including 90 calendar days after the last administration of study treatment (Arm A) or 90 days after the EOT visit (Arm B).

If a patient begins a new anticancer therapy, the AE reporting period for non-serious AEs ends at the time the new treatment is started. Death must be reported if it occurs during the SAE reporting period after the last dose of study treatment, irrespective of any intervening treatment.

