5.2.7. Definition of on-treatment period

Safety endpoints will be summarized based on the on-treatment period unless otherwise specified. On-treatment period is defined as follows:

- Arm A: time from the first dose of study treatment through minimum (30 days + last dose of study treatment, start day of new anti-cancer drug therapy – 1 day);
- Arm B: time from Cycle 1 Day 1 through minimum (30 days + end date of BSC, start day of new anti-cancer drug therapy – 1 day).

Here, 'end date of BSC' is the date of completion or discontinuation as collected in the 'Disposition - Treatment Phase' eCRF page.

Safety data collected outside the on-treatment period as described above will be listed and flagged in listings but will not be summarized.

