6.5.3.1. Exposure to avelumab

The dose level for avelumab is calculated as actual dose administered/weight (mg/kg). The last available weight of the patient on or prior to the day of dosing will be used.

For Cycle X, actual cycle start date for each patient is

- the start date of dosing in the Cycle X day 1 visit eCRF exposure page, if the patient received avelumab on that visit (ie, avelumab with dose>0 at that visit)

- the first day of assessments in the Cycle X day 1 visit, if the patient did not receive avelumab on that visit (ie, dose=0 for avelumab at that visit). Use start date in the exposure page if available; if start date is not available then use date of collection of vital signs on Cycle X day 1 visit.

Actual cycle end date for each patient is,

- for all cycles X except the last cycle, actual cycle end date = actual cycle (X+1) start date – 1 day;
- for the last cycle, actual cycle end date = actual cycle start date + 28 – 1 day

Cycle duration (weeks) = (actual cycle end date – actual cycle start date + 1)/7

Intended duration of treatment with avelumab (weeks) =

(end date – date of first dose of avelumab + 1)/7,

where end date = start date of last cycle with non-zero dose of avelumab + 28 – 1

Duration of exposure to avelumab (weeks) =

(last dose date of avelumab – first dose date of avelumab + 14)/7

Cumulative dose is the sum of the actual doses of avelumab received.

Actual Dose Intensity (DI)

- Overall actual DI (mg/kg/4-week cycle) = [overall cumulative dose (mg/kg)] / [intended duration of treatment with avelumab (weeks)/4].

Relative Dose Intensity (RDI)

- Intended DI (mg/kg/4-week cycle) = [intended cumulative dose per cycle] / [intended number of 4-weeks in a cycle] = [20 (mg/kg)] / [1 (4-week cycle)] = 20 (mg/kg/4-week cycle)
- Overall RDI (%) = $100 \times [\text{overall actual DI}] / [\text{intended DI}]$
= $100 \times [\text{overall actual DI}] / [20 \text{ (mg/kg/4-week cycle)}]$

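### The SAP has no re-treatment course, so for patients who restart avelumab the drug-free gap is counted in exposure, dose intensity, dose delay and the on-treatment period

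*SAP*

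**What the plan says.** **Protocol 5.4.1.** A patient who stops avelumab and then progresses radiologically "will be eligible for re-treatment with avelumab at the discretion of the investigator", after discussion with the sponsor's medical monitor. Three conditions apply: "no cancer treatment was administered other than BSC since the last dose of avelumab", the safety withdrawal criteria are not met, and the trial is still open. Under Amendment 6, after the final OS update, such patients "will no longer be eligible for re-treatment with avelumab". That wording implies that the option was open until then.

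**SAP.** No section mentions re-treatment or divides dosing into courses. The relevant rules for Arm A are:

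- Section 3.4.1, last dose: "The date/time of last dose of study treatment is the latest date/time of non-zero dosing of the study drug".
- Section 5.2.7, on-treatment period: first dose through the earlier of last dose + 30 days and the day before new anti-cancer drug therapy. Outside it, "Safety data collected outside the on-treatment period as described above will be listed and flagged in listings but will not be summarized".
- Section 6.5.3.1, duration of exposure: (last dose date − first dose date + 14)/7 weeks.
- Section 6.5.3.1, intended duration (the dose-intensity denominator): counted from the first dose, "where end date = start date of last cycle with non-zero dose of avelumab" plus 28 − 1 days.
- Section 6.5.3.3, dose delay: the interval between consecutive non-zero doses minus 14 days.

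**Collection of safety data.** Protocol 8.2 has AEs recorded in Arm A up to 90 days after the last administration. The follow-up Schedule of Activities places laboratory tests, ECOG and AEs at end of treatment and at 30, 60 and 90 days. Long-term follow-up covers survival, tumor assessment and new anticancer treatment.

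**The concern.** The protocol treats stopping avelumab and restarting it as separate events, while the SAP formulas see one run of doses from the first to the latest. The only rule that could close the on-treatment window early is the start of new anti-cancer drug therapy. That cut cannot apply during the gap, because re-treatment requires that no such therapy was given.

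Two things are at stake. Exposure and dose-intensity tables would show long exposure with poor delivery for a patient who missed no dose within either course. Safety data collected off drug, more than 30 days after the first course ended, would enter the treatment-emergent AE, worst-grade laboratory and ECOG-shift summaries if the patient later restarts. The same data would only be listed if the patient does not restart. Classification then depends on a later treatment decision, and BSC alone has no counterpart to it.

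**Working it through.** **1. The plan's own figures.** Intended dose intensity is 2 doses × 10 mg/kg = 20 mg/kg per 4-week cycle, as SAP 6.5.3.1 states. A dose on Day 16, 17 or 18 after a Day 1 dose gives 16 − 1 − 14 = 1, then 2 and 3 days of delay, matching the example in SAP 6.5.3.3. An uninterrupted 8-cycle patient gives 32 weeks of exposure, 100% relative dose intensity (RDI) and no delay. The formulas work as intended within one course.

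**2. Assumed re-treated patient.** The documents give no gap length, so this is an illustration:

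- 12 doses on days 1 to 155 (24 weeks).
- A 40-week drug-free gap.
- 6 doses on days 449 to 519 (12 weeks).
- Every scheduled dose within each course is given; cumulative dose 18 × 10 = 180 mg/kg.

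Re-treatment doses are assumed to be recorded on the same avelumab exposure pages as the first course.

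**3. SAP formulas against a course-by-course count.**

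| Quantity | SAP formula | By course |
|---|---|---|
| Exposure | (519 − 1 + 14)/7 = 76 weeks | (155 − 1 + 14)/7 + (519 − 449 + 14)/7 = 24 + 12 = 36 weeks |
| Intended duration | last cycle starts day 505, ends 505 + 28 − 1 = 532; 532/7 = 76 weeks | 36 weeks |
| Dose intensity | 180/(76/4) = 9.47 mg/kg per 4 weeks | 180/(36/4) = 20 |
| RDI | 9.47/20 = 47% | 100% |
| Longest delay | 449 − 155 − 14 = 280 days | 0 within either course |
| On-treatment | days 1 to 549 = 549 days | days 1–185 and 449–549 = 185 + 101 = 286 days |

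The extra on-treatment time is 549 − 286 = 263 days (days 186 to 448).

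**4. How much of the extra time carries data.** Routine AE recording from the first course ends on day 155 + 90 = 245. Days 246 to 448 (203 days) have none. That leaves 263 − 203 = 60 days (186 to 245) of routinely recorded AEs, with the 60- and 90-day laboratory and ECOG visits. Later SAEs that the investigator learns of, and assessments before re-dosing, can add to this.

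**5. Sensitivity to the gap.** Assumed patient with 6 full cycles, a gap, then 2 full cycles (16 doses, 160 mg/kg). By course, the results are 32 weeks, 100% RDI, no delay and 258 on-treatment days, whatever the gap.

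| Gap (weeks) | Exposure (weeks) | RDI | Longest delay (days) | On-treatment (days) | Excess (days) |
|---|---|---|---|---|---|
| 12 | 44 | 72.7% | 84 | 325 | 67 |
| 26 | 58 | 55.2% | 182 | 423 | 165 |
| 52 | 84 | 38.1% | 364 | 605 | 347 |

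**The case against.** **First-to-last exposure is a coherent convention.** An RDI of 47% correctly describes drug delivered per calendar time since the first dose, and the course-based figures are another presentation, not the only true one. This stands as a point of definition. It is less persuasive where the protocol itself separates stopping from re-treatment, because the tables give the reader no way to tell a restart from poor delivery.

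**A reader might infer that the whole gap floods the safety tables with events at progression.** The documents do not support that. Laboratory tests, ECOG and AEs are scheduled only to 90 days after the last dose, and Protocol 8.3 excludes radiographic progression from AE reporting. The long gaps that distort exposure most add mainly empty time to the safety window.

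**A reader might also infer that a planned treatment break is misreported as a delay.** The protocol has no planned stop. Under its section 3.1.1, treatment continues until progression, refusal, loss to follow-up, toxicity or termination. A re-treated patient simply falls in the category of 7 or more days.

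**The bias adds events to the avelumab arm, and the pool is small.** Extra events do run against avelumab, and the SAP describes safety analyses as generally exploratory. Several conditions must be met, and the patient must have stopped before radiologic progression. All of this limits the consequence. It does not correct the overstated exposure or the lowered RDI.

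**Conclusion.** The point holds as a gap between a protocol provision and the SAP's stated rules. For re-treated avelumab patients the drug-free interval enters exposure and the dose-intensity denominator, becomes one long delay, and lies inside the on-treatment period. In the 40-week illustration, exposure roughly doubles (76 against 36 weeks) and RDI roughly halves (47% against 100%). These sizes rest on assumed dosing patterns and gap lengths.

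The safety effect is narrower: mainly data from 31 to 90 days after the first-course last dose, summarized for re-treated Arm A patients and otherwise only listed. A claim that the overall safety comparison is compromised would need the number of re-treated patients, which the documents do not give and which may be small. OS, the alpha split and the sample size are untouched. This is a worthwhile clarification, not a threat to the trial's conclusions.

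**What to change.** Amend SAP 3.4.1, 5.2.7 and 6.5.3 as follows:

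- The initial course ends at the last non-zero dose before the recorded study-drug discontinuation. The re-treatment course starts at the next non-zero dose.
- Gap length alone should not separate courses, because doses may be withheld for toxicity (Protocol Table 3 allows up to 12 weeks from the last administration for recovery).
- Exposure, RDI and dose delay are computed within course.
- On-treatment is the union of the course windows, each from first dose to last dose + 30 days and cut at new anti-cancer drug therapy.
- AEs with onset in a re-treatment course are flagged, and the number of re-treated patients is reported.

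The cost is SAP wording and one derived variable. It depends on the sponsor confirming that the first discontinuation date is retained in the eCRF after a restart. SAP 6.5.2.1 plans to summarize study-drug discontinuation, but the documents do not show how that record behaves for re-treated patients. The change is analytical only and alters no treatment rule.
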